#### 7.1.2 Healthy volunteers

For recruitment of normal participants or healthy volunteers, posters/flyers will be placed on bulletin boards at the study site (Mount Sagarmatha Polyclinic).

### 7.2 Inclusion and Exclusion Criteria

#### 7.2.1 Inclusion Criteria

Since the techniques evaluated in the study aims at detecting sickle cell disease (SCD), sickle cell trait (SCT), and  $\beta$ -thalassemia, the following number of participants will be included in the study:

- 20 individuals with SCD (HbSS)
- 20 individuals with SCT (HbAS)
- 20 individuals with sickle cell/β-thalassemia compound heterozygous form (HbS/β-thalassemia)
- 20 individuals with β-thalassemia (Hbβ/β-thalassemia)
- 20 individuals with β-thalassemia trait or carrier form (HbA/β-thalassemia)
- 20 healthy individual participants or normal participants (HbAA, participants without any known hemoglobin disorders, such as SCD, SCT or β-thalassemia)

Participants older than 1 year of age at the time of drawing blood will be eligible. Signed and dated consent or assent forms will be required by the participants or their parents/guardians.

#### 7.2.2 Exclusion Criteria

The exclusion criteria for the study:

- Transfusion within the last 3 months
- Pregnancy

Participants who wish to withdraw from the study will also be excluded.

#### 7.3 Consent and Assent

#### 7.3.1 Consent process

Informed consent will be obtained by study coordinator or delegate during in-person visits. Written consent and assent forms will be provided in Nepali and will be signed and dated by participants or by guardians/parents of participants. For all participants, signed consent forms (hard copy) will be used as documentation for consent. All the consent forms will be signed inperson by pen on physical copies of the form. All participants will receive physical copies of the consent forms, while the researchers will retain physical copies of the signature pages with the corresponding version names and dates (duplicate or counterpart copies). The physical copies (duplicates) of the consent forms will be stored in a secure location in Mount Sagarmatha Polyclinic and Diagnostic Center (e.g. in [name] office), and [name] (the investigator in Nepal) will have access to the physical copies. The consent forms with identifiable information of participants will not be transferred to UBC or Canada, and only the deidentified information (including unique participant codes) will be transferred to Canada, along with the de-identified data (e.g. images of blood films, test results, demographic information).

Assent forms and adolescent assent forms will be provided to children between 7-13 years and 14-18 years, respectively. The consent and assent forms will be stored separately from deidentified data, and the de-identified data will only be referred using unique participant codes. It will be emphasized that participation is completely voluntary and provision of care will not be affected should any patients associated with the hospital/clinic decline to participate.

#### 7.3.2 Free, informed and ongoing consent

Participants will be clearly informed about the risks and benefits of the research, and informed about context of the current study in terms of the overall project. They will be informed that deidentified images of blood films will be used to train machine learning algorithms and publicly stored in an online database created in the Federated Research Data Repository (FRDR), an initiative by the Digital Research Alliance of Canada.. In accordance with the Declaration of Helsinki, Good Clinical Practice (GCP) guidelines and the Tri-Council Policy, a subject has the right to withdraw from the study at any point and for any reason, in which case, results and collected data will be removed and excluded from analyses.

Personal identifiers, such as names, date of birth, personal health number, etc. will not be disclosed in the study. Demographic information, such as age, sex and race, will be recorded and reported to account for and represent different distributions of hemoglobinopathies in different populations. If willing, participants can disclose their age, sex and race in a separate questionnaire. Although demographic data is available through the records of the hospital/clinic, the data for this study (age, sex and race) will only be collected through a questionnaire. The questionnaire does not collect any personal identifiers and is linked to the study ID or the unique participant codes. The data will be entered in the data collection form (Excel) and saved in password protected and encrypted computers and hard drives. To indicate the optional nature of the fields in the questionnaire, a checkbox with "Prefer not to answer" will be provided for age, sex and race. Since most of the population in the study will be from South Asian descent, this option will be provided along with "Other", "Do not know", and "Prefer not to answer". The reason for collection and dissemination of demographic information will be explained in the consent forms and questionnaires.

# 7.4 Blood drawing and de-identification of blood samples

Certified phlebotomists will use the standard technique currently being used to draw blood at the hospital/clinic, with no special changes related to this study. A sample technique (which could vary slightly) is provided - The antecubital fossa will be identified and sterilized with an alcohol based sanitizer. After application of the tourniquet, blood will be drawn primarily from the median cubital vein. If this vein is difficult to identify or collect a sample from, other veins in the antecubital fossa will be used (cephalic vein or basilic vein). The vein will be punctured using a winged or butterfly hypodermic needle, and around 3-4 mL of blood will be collected in an evacuated container (e.g. Vacutainer) pre-loaded with anticoagulant (such as ethylenediaminetetraacetic acid or EDTA). For young children, if the veins of the antecubital fossa are not identifiable, dorsal metacarpal veins will be used. The status of the patient will be checked to confirm that bleeding has stopped. The container with the collected blood will be labelled and transported securely.

The blood samples collected will be associated with unique participant codes with no identifiable patient information. The participant code will contain details of the site of collection, date collected, and a serial number or time collected. For instance, the code 'MSP-20220502-001' indicates the first blood sample collected at Mount Sagarmatha Polyclinic on 02 May 2022. The study team members will be provided with only the codes, and data will be analyzed using the code as the main label or reference. Blood samples labels, images, test results, etc. will all be associated only with the unique codes, and not contain identifiable information.

Only the doctors/staff at the respective collection sites will have access to the reference list of personal identifiers (such as name, date of birth, health number) linking to the corresponding codes or de-identified data. The list will be stored in encrypted files in password protected

computers. This list will not be shared with the other study team members and the list is not required for analysis. Demographic data such as age, sex and race will be shared and reported only to properly identify the population represented in the study, and this will be clearly indicated in the consent/assent forms.

Images taken of blood will contain no identifiable information and will only reference the codes or de-identified data. Additionally, the information contained in the microscope images, which mainly includes the morphology of blood cells before or after adding reagents, cannot be linked back to any of the participants.

#### 7.5 Sample preparation and tests

Sample preparation and tests will be performed in the hematology lab at Mount Sagarmatha Polyclinic by study team members and/or qualified hospital staff/technicians. Study team members preparing reagents and blood samples will have appropriate personal protective equipment (PPE) as determined by lab protocols. All study team members working with blood samples will have completed the necessary training required to work in the hematology lab (e.g. UBC Biological Safety, UBC Chemical Safety, PHSA safety courses, etc.). All work surfaces will be decontaminated after sample preparation, and contaminated laboratory material (e.g. pipette tips) will be disposed in a sharps/biohazard container.

#### 7.5.1 Sickling Test

The methods used for the sickling test are as follows:

## Reagent (2% sodium metabisulphite) preparation

- Add 0.2 g of sodium metabisulphite to 10 mL of distilled water in a vial/container
- Mix or stir till dissolved
- Prepare fresh every time (and use within 3 hours)

#### Microscope slide preparation

[figure not shown]
- Mix 1 drop of blood with 1 drop of 2% sodium metabisulphite on a microscope slide
- Add cover slip
- Incubate at room temperature for 30 minutes

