# Evaluation of low-cost techniques for detecting sickle cell disease and $\beta$ -thalassemia in Nepal

# 1.0 Background

## 1.1 Sickle cell disease

Sickle cell disease (SCD) is a collection of inherited blood disorders, and is a multisystem disorder affecting nearly every organ in the body [1]. The disease primarily causes erythrocytes or red blood cells (RBCs) to be distorted and rigid due to polymerization (e.g. during deoxygenation), often changing them to crescent or sickle shaped cells [2]. Other cascading effects include hemolytic anemia, blockage of microvasculature (capillaries and small blood vessels), episodes of acute illness (such as vaso-occlusive pain crisis or sickle cell crisis), and progressive organ damage [3], [4]. The chances of survival and quality of life drastically increase with early diagnosis, newborn screening, penicillin prophylaxis, pneumococcal immunization, blood transfusion, hydroxyurea treatment, hematopoietic stem-cell transplantation, and education about disease severity and complications [1], [4].

SCD is one of the most common monogenic diseases worldwide and results from mutations in the  $\beta$ -globin gene [1], [3]. The most common and severe form of SCD is sickle cell anemia (SCA), caused by the inheritance of  $\beta^S$  alleles or the variant HbS (hemoglobin S or sickle hemoglobin) genes from both parents – resulting in the homozygous form HbSS, instead of the normal homozygous form HbAA. Another form of SCA is HbS/ $\beta^0$  thalassemia, caused by the inheritance of a  $\beta^0$  thalassemia mutation from one parent and an HbS gene from another, resulting in no normal HbA and a majority of HbS. The heterozygous form HbAS, known as sickle cell trait (SCT), affects millions of people worldwide and is usually not associated with hematological abnormalities [2]. On the other hand, compound heterozygous conditions are associated with mild to severe clinical courses and are also categorized as SCD. Some compound heterozygous conditions include HbS with hemoglobin C or HbC (HbSC), HbS with  $\beta$ -thalassemia (HbS/ $\beta^0$ -thalassemia or HbS/ $\beta^+$ -thalassemia), and HbS with other  $\beta$  globin variants (e.g. HbSD and HbSOArab) [1], [3], [4].

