# 3.0 Hypothesis

We hypothesize that

1. Gazelle diagnostic device can detect  $\beta$ -thalassemia and SCD/SCT with an overall accuracy greater than 90%, compared with HPLC as the reference test

- 2. an automated sickling test (standard sickling test enhanced using low-cost microscopy and machine learning) has a higher overall accuracy than conventional screening techniques (solubility and sickling tests) to detect hemoglobin S in blood samples
- 3. the automated sickling test can additionally classify SCD, SCT and healthy individuals with a sensitivity greater than 90%, based on morphology changes of red blood cells, unlike conventional sickling or solubility tests that do not distinguish between SCD and SCT cases

Overall, we hypothesize that an assessment of the performance and accuracies of low-cost point-of-care techniques (automated sickling test, solubility test, lateral-flow assays, Gazelle Hb variant test) against HPLC tests will provide researchers and health workers with feasible alternative options for screening and detecting SCD, SCT and  $\beta$ -thalassemia in a variety of situations based on the needs of the communities and the resources available.

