#### Testing procedure [2]

- Add 2 mL of reagent to three test tubes using a pipette
- Let reagent warm to room temperature
- From EDTA container, add 10 µL of packed cells to one tube
- Create positive control using 10 μL of packed cells from known SCT patient (HbAS) to second tube
- Create negative control using 10 μL of packed cells from a known normal subject (HbAA) to third tube
- Mix the blood-reagent mixture well and let stand for 5 minutes
- Ensure that the blood-reagent mixture is light pink or red (a light orange color appears if the reagent has deteriorated)
- Place tubes 2.5 cm in front of a white sheet with narrow black lines
- Compare the turbidity with positive and negative controls
- The test is positive if the solution is turbid (black lines are not observed through the solution), and is similar to the positive control, as shown in Figure 2
- The test is negative if the solution is clear (black lines are observed through the solution), and is similar to the negative control, as shown in Figure 2

[figure not shown]

Figure 2 | Results of the HbS solubility test showing (from left to right) a positive control (turbid), a negative control (clear), a positive test (turbid) and a negative test (clear) [13]

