# 7.8 Neural Network Training and Testing

Data manipulation and analysis will be done through Python. All software to be utilized is opensource and does not have commercial implications. In order to optimize the screening algorithm, multiple neural network configurations will be tested and compared. All the models tested for classification will use existing pre-trained models that have applications in image classification. In each case, the acquired images will be split into three groups, consisting of training data (around 80%), validation data, (around 10%) and testing data (around 10%). The data will be used to train the neural network using a pre-trained supervised machine learning model, whereby the images are input and the parameters of the network are optimized to classify images by hemoglobin phenotype. The test data will test the performance of the trained network on images that have not been used for training. We will use the neural networks most commonly used for medical image classification, such as EfficientNet, ResNeXt, ResNet-50, DenseNet, and Xception. When possible, training will occur locally on the laboratory computer at UBC. For networks that require additional computing power, UBC ARC Sockeye or Compute Canada will be used.

All the machine learning algorithms will only include de-identified data, such as images of blood films and hemoglobin phenotype (such as sickle cell trait or HbAS). Personal identifying information, such as participant names, will not be associated with any of the data used for analysis or stored online.

Cloud computing facilities, such as those from Compute Canada, will be utilized to train and test machine learning algorithms on the final dataset of images. Compute Canada is a cloud computing service provided by Digital Research Alliance of Canada (the Alliance) to Canadian research institutions. The servers and clusters (e.g. Cedar cluster located in BC) will be accessed using Secure Shell Protocol (SSH). For the analysis (before sharing the data publicly), de-identified images may be stored securely in UBC servers or in servers for Compute Canada.

The de-identified data (such as images of blood films and associated de-identified data like hemoglobin phenotype) will be deposited in an online public repository, such as Federated Research Data Repository.

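### Cell density is uncontrolled on the sickling slides and may track SCD versus SCT, so sensitivity above 90% would not by itself show that the network separates them by morphology, as Hypothesis 3 states

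*Combined protocol and SAP*

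**What the plan says.** - Section 3.0, Hypothesis 3, makes a claim about mechanism as well as accuracy: the automated sickling test can "classify SCD, SCT and healthy individuals with a sensitivity greater than 90%, based on morphology changes of red blood cells". Section 1.6 (Machine Learning) likewise names morphology as the basis for separating SCD from SCT, and calls this an aim of the study.
- Section 7.5.1 prepares the slide as follows: "Mix 1 drop of blood with 1 drop of 2% sodium metabisulphite on a microscope slide". A cover slip is added and the slide is incubated. Drop volumes are not measured, and no step brings samples to a common haematocrit or cell count.
- Section 1.1 says of SCD: "Other cascading effects include hemolytic anemia". It says that SCT "affects millions of people worldwide and is usually not associated with hematological abnormalities".
- Section 7.8 describes the training: "the images are input and the parameters of the network are optimized to classify images by hemoglobin phenotype". HPLC supplies the ground truth. The background (Section 1.6) describes cell-by-cell segmentation as the usual first step, but 7.8 does not adopt it. Nor does 7.8 mention density matching, a haematocrit covariate, or any check of which image features the network uses.
- Section 13 says the analyses will take account of treatment and medication, and it discusses haplotype and HbS/β-thalassemia. It does not mention anaemia or cell density.

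**The concern.** If SCD participants are anaemic and SCT participants mostly are not, their films will tend to hold fewer cells per field. That difference is visible in every whole image and runs in the same direction as the HbSS/HbAS label. A network trained on images and labels alone may use it. Having recognised that sickling is present, it could divide SCD from SCT by how crowded the film is rather than by how the sickled cells look.

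The interpretation of Hypothesis 3 is at stake. A sensitivity above 90% would fit a morphology effect, a density effect or a mixture, and nothing in the plan separates them. The distinction matters later, because Section 4.0 lists use of the trained algorithm in screening in Nepal as a long-term objective. A classifier that leans on density could call an anaemic person with SCT SCD, or call a less anaemic person with SCD SCT. With about 20 HbAS participants and no density or haematocrit recorded, the study would be unlikely to reveal this.

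**Working it through.** The plan gives no figure on this point to reproduce. The check has two parts.

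**1. Does the slide preparation remove a density difference?**

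Let a sample's cell density be H. Mixing equal drops of blood and reagent gives H/2. For two samples the ratio after mixing is (H₁/2)/(H₂/2) = H₁/H₂. The mixing step leaves the between-group ratio as it was. Unequal drops add noise but do not correct for anaemia.

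**2. How far could density alone separate HbSS from HbAS?**

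The documents give no haemoglobin, haematocrit or film-noise figure, so every input here is an assumption shown over a range. The cut-off is placed so that sensitivity equals specificity. HbSS and HbAS are then each classified correctly at the same rate, which is the relevant comparison for a claim covering both classes.

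*Model A: log-normal density.* R is the HbSS/HbAS density ratio, c the between-person CV, and v the CV from unmeasured drops.

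- Separation: d = −ln(R) / √[ln(1+c²) + ln(1+v²)]
- Sensitivity = specificity = Φ(d/2)
- To reach 90%: d = 2 × 1.2816 = 2.56

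| R | c | v | d | sens = spec |
|---|---|---|---|---|
| 0.9 | 0.15 | 0.3 | 0.32 | 56% |
| 0.8 | 0.10 | 0 | 2.24 | 87% |
| 0.7 | 0.10 | 0 | 3.58 | 96% |
| 0.7 | 0.10 | 0.1 | 2.53 | 90% (89.7%) |
| 0.7 | 0.10 | 0.3 | 1.15 | 72% |
| 0.6 | 0.10 | 0 | 5.12 | 99.5% |

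The full grid has R = 0.6, 0.7, 0.8, 0.9; c = 0.10, 0.15; and v = 0, 0.1, 0.2, 0.3, which is 4 × 2 × 4 = 32 combinations. Of these, 5 exceed 90%.

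*Model B: normal haematocrit.* SD is 4 points, HbAS mean 40%, HbSS mean m, with multiplicative film noise. Without noise, sensitivity = specificity = Φ[(40 − m)/(2 × 4)]. For m = 25 this is Φ(1.875) = 97%. With noise the figures come from simulation.

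| HbSS mean | CV 0 | CV 10% | CV 20% | CV 30% |
|---|---|---|---|---|
| 25 | 97.0% | 92.5% | 83.5% | 76% |
| 28 | 93.3% | 87.1% | 77.6% | 71% |
| 30 | 89.4% | 82.5% | 73.2% | 67% |

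Of the 12 scenarios, 3 exceed 90%.

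Both models say the same thing. Density could contribute substantially, and under strong anaemia with little film noise it could reach the target unaided. Under milder anaemia or noisier drops it falls well short.

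**The case against.** Several parts of the opposing case stand.

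- **Detecting sickling is itself a judgement of shape.** Section 7.5.1 reads a slide by the share of cells that look sickled or deformed. Separating HbAA from HbS carriers therefore still needs morphology, and only the SCD-versus-SCT step is open to a density shortcut.
- **Accuracy in this sample is not biased.** Sensitivity and specificity against HPLC describe whatever the classifier does. Objective 2 in Section 4.0 asks only whether the groups can be classified from the images, so it could be met whatever the mechanism.
- **No size is documented.** Unmeasured drops add noise that weakens the shortcut, so high film noise cannot be dismissed.
- **Field use is downstream.** Section 7.8 says the algorithm will not diagnose new patients in this study.

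A reader might infer more from three other features, and the documents do not support these readings:

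- The blood is not undiluted. It is mixed about 1:1 with reagent.
- The imaging studies cited in Section 1.6 used diluted blood, but a fixed dilution preserves the density ratio just as the 1:1 mix does. Nothing in the protocol says those studies equalised cell counts.
- The solubility test does use packed cells ("From EDTA container, add 10 µL of packed cells to one tube"). But Section 6.3 makes phenotype analysis not applicable to it, so it is no comparator for the SCD/SCT separation.

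It could also be said that anaemic β-thalassemia participants break the link between a sparse film and HbSS. They do so only for a rule that uses density alone across all groups. A network that first recognises sickling and then uses density to divide HbSS from HbAS is not hindered by anaemic participants without HbS.

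None of this answers the central point: nothing planned separates density from morphology as the basis of the SCD/SCT division.

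**Conclusion.** The concern holds as a limit on interpretation. Density is uncontrolled, the protocol's description of SCD and SCT implies that it may differ between them, and Section 7.8 contains nothing to isolate morphology. Sensitivity above 90% would not by itself show that the SCD/SCT separation is "based on morphology changes of red blood cells".

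A reader might go further and conclude that the network will merely learn anaemia, or that density is enough to meet the 90% target. The documents do not show either. The range of about 56% to 99% rests wholly on assumed density ratios, between-person variation and film noise, and most of the assumed scenarios fall below 90%. The point concerns the mechanism stated in Hypothesis 3 and the transfer of the classifier to differently anaemic people. HbS detection, HPLC-referenced accuracy in this sample and Objective 2 as worded are not affected. It is worth correcting because the remedy is cheap and needs only the images already planned.

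**What to change.** Add to Section 7.8:

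1. Compute cells per field for every image.
2. Using cross-validation with whole participants held out, report HbSS-versus-HbAS accuracy, with confidence intervals, for a classifier given density only, beside that of the network.
3. As a sensitivity analysis, repeat the network analysis on single-cell crops or density-matched patches.
4. Attribute the SCD/SCT separation to morphology only if performance is retained in step 3. Otherwise report it as image-based classification and drop the morphology wording from the conclusion on Hypothesis 3.

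Cross-validation is needed because a single 10% test set, if split by participant, holds about 0.10 × 120 = 12 people, or 0.10 × 20 = 2 per group. For the same reason the network should not be required to beat the density classifier on held-out participants. A tie at high accuracy would not refute morphology in any case. Even with all 20 in a group, 18 of 20 correct has an exact (Clopper–Pearson) 95% interval of about 68% to 99%, so the side-by-side comparison should be read descriptively.

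The cost is some analysis code and a few sentences in 7.8. Slide preparation, samples and staffing stay as they are. The downsides are that the sensitivity analysis discards some image data and that the reported SCD/SCT accuracy may be lower.
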